4.2 Overall Response Rate (ORR)

Overall response is determined by investigator assessment for each tumor assessment in the study. For patients with solid tumors, the assessment criteria will be RECIST 1.1 and will include responses of CR and/or PR. For hematological tumors, other appropriate criteria (see Protocol Appendix section for corresponding criteria) will be used to determine the responses. Ninety-five percent (95%) exact CI will also be provided for the response rates. The number and percentage of patients for different categories of overall response (e.g., for solid tumor - CR, PR, SD, PD, and NE) will be presented. These analyses will be performed with all solid tumor types combined and separately for each hematological tumor type. For tumor types that have ten (10) or more patients (within the solid tumors), separate summaries will be performed by the tumor type. In the event that there are fewer than 4 patients for a hematological tumor type, only listing will be provided for that tumor type.

Components of tumor assessments (target lesion response, non-target lesion response, new lesion [yes/no]) will be listed. In addition, Cancer Antigen-125 (CA-125) in the assessment of ovarian cancer response, or Prostate-specific antigen (PSA) in the assessment of prostate cancer response will also be listed.

4.3 Duration of response

DOR applies only to patients who responded, e.g., for solid tumor, responder is defined as the patient's best overall response being CR or PR. The start date is the date of first documented response, and the end date is the date of event defined as the first documented progression/relapse or death due to any cause within 30 days of the last study drug dose date. In other words, the start date will be determined using the time the response was first determined and not using the time the response was confirmed. If a patient has not had an event, duration is censored at the date of last adequate tumor assessment. Distribution of DOR will be estimated using the Kaplan-Meier method and the median response duration will be

presented along with 95% confidence interval only if there are sufficient numbers of events, otherwise, only listing of DOR will be provided. Analyses will be based all tumor types combined.

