4.1 Clinical Benefit Rate (CBR)

Clinical benefit is determined by investigator assessment for each tumor assessment and is defined as responses of CR or PR or SD for ≥ 16 weeks. In addition to tumor-specific measurements (e.g., radiological assessment of tumor response for solid tumors), progressive disease will also be considered when it was indicated either as a reason for the study treatment

discontinuation or as a cause of on-treatment death. CR and PR (for solid tumors) require a confirmation that is at least a minimum of 4 weeks after the initial observation of response. Patients who had confirmed CR/PR or SD prior to 16 weeks, but discontinued prior to 16 weeks for reasons other than progressive disease, will have their clinical benefit defined as non-evaluable; patients who had confirmed CR/PR or SD prior to 16 weeks, but progressed prior to 16 weeks, will be considered as not achieving clinical benefit; patients who had CR/PR/SD occurred prior to 16 weeks, but progressed at or after 16 weeks without evidence of CR/PR/SD at or after 16 weeks, will also be considered as not achieving clinical benefit. CBR will be analyzed by comparing achieved CBR with a historical control rate of each tumor type, and if there is at least 80% probability that the response rate in a tumor type exceeds the historical rate, then the tumor type will be considered a success. Details for the Bayesian analyses of CBR are located in Section 8.

In addition to the Bayesian analyses, with all solid tumor types combined and separately for each hematological tumor type, the CBR estimate will be provided with its 95% exact CI. For tumor types (within the solid tumors) that have ten (10) or more patients, separate summaries will be performed by the tumor type. In the event that there are fewer than 4 patients for a hematological tumor type, only listing will be provided for that tumor type.

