4.4 Progression Free Survival (PFS)

PFS is defined as the time from the date of first dose of ribociclib to the date of the first documented disease progression/relapse or death due to any cause within 30 days of the last study drug dose date, and is calculated as $PFS = (\text{date of progression/relapse or death} - \text{date of first study treatment} + 1)$. Disease progression noted as the reason for discontinuation of treatment will also be considered as a progression event for PFS analyses.

Patients who discontinue or complete study treatment without disease progression will be censored at last adequate tumor assessment on or before the discontinuation/completion of the study. For patients who are still on study treatment at the time of data cut-off date for the primary analyses, PFS will be censored at the last adequate tumor assessment before the data cut-off date for the analysis of PFS for the primary CSR. Patients who do not have any post baseline tumor assessment will be considered as censored at Day 1.

PFS will be summarized and graphed using the Kaplan-Meier product-limit method². The estimated median survival time, the corresponding 95% CIs³, and 25th and 75th percentiles will be provided. In addition, survival-rate estimates with 95% CIs will also be provided at time points, such as 1, 2, 3, 4, 5, 6, 9 and 12 months. Analyses will be based on all tumor types combined. For tumor types that have ten (10) or more patients, separate summaries will be performed by the tumor type.

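### A responder who stops treatment for progression without a progression scan is an event for PFS but is censored for duration of response (SAP 4.3 against 4.4)

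*SAP*

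**What the plan says.** SAP 4.3 (duration of response) starts at the first documented response and ends so: "the end date is the date of event defined as the first documented progression/relapse or death due to any cause within 30 days" (counted from the last dose). For everyone else: "If a patient has not had an event, duration is censored at the date of last adequate tumor assessment".

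SAP 4.4 (PFS) uses the same base event, documented progression or relapse, or death within 30 days of the last dose. It then adds: "Disease progression noted as the reason for discontinuation of treatment will also be considered as a progression event for PFS analyses".

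SAP 4.1 (clinical benefit) has a similar provision: "progressive disease will also be considered when it was indicated either as a reason for the study treatment" discontinuation or as the cause of an on-treatment death. SAP 4.3 has neither sentence.

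Protocol 10.5.2 gives PFS and DOR the same terminating event. SAP 2.3, which lists departures from the protocol, does not mention the addition made in 4.4.

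**The concern.** For a responder, PFS and DOR should end at the same event on the same date; only the starting points differ. Here one endpoint accepts progression recorded as the stopping reason and the other does not. A responder taken off drug for progression without a scan showing it is a PFS event, but for DOR is censored at the last scan, when still in response.

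Kaplan-Meier estimation assumes that a censored patient has the same outlook as those who remain at risk. These patients are censored because they have just progressed, so the assumption fails and DOR looks longer than it is. The two endpoints also disagree about the same patients, which a reader of the report would see.

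**Working it through.** The plan states no figure to reproduce. The check has three parts.

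**1. Can the case arise?**
- Protocol 4.1.1 asks that progression leading to discontinuation be clearly documented. Protocol 7.2.1 asks for prompt assessment when progression is suspected.
- Table 7-1 note 3 requires an end-of-treatment scan if the patient stops before the first scheduled scan, or if the last scan without progression was at least 8 weeks earlier. A responder who stops within 8 weeks of such a scan is not covered.
- After week 16, scans are 16 weeks apart, so about half of each interval carries no end-of-treatment scan requirement.
- Protocol 7.1.4.2 has no efficacy follow-up, so no later protocol scan recovers the event.
- SAP 4.1 and 4.4 themselves provide for the case.

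**2. Size of the bias in the 26-week DOR rate.** Assumptions, none from the documents except the scan schedule and note 3:
- response is first seen at week 8, so later scans fall 8, 24 and 40 weeks into the response;
- true DOR is exponential with median m weeks, S(t) = 2^(−t/m);
- a share f of progressions is recorded only as the stopping reason, unless the last scan was 8 or more weeks earlier, when the end-of-treatment scan documents it;
- all other progressions are dated at the next scan.

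With the PFS rule: (1−f)·S(24) + f·S(26).

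Under SAP 4.3 as written:
- A = 1 − (1−f)(1−S(8)) / [1 − f(1−S(8))]
- n = S(8) − f[S(8)−S(16)]
- d = (1−f)[S(8)−S(24)] + f[S(16)−S(24)]
- rate = A·(1 − d/n)

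Example, m = 24 and f = 0.20: S(8) = 0.794, S(16) = 0.630, S(24) = 0.500, S(26) = 0.472.
- With the rule: 0.8×0.500 + 0.2×0.472 = 0.494.
- Without it: A = 0.828, n = 0.761, d = 0.261, rate = 0.828×(1 − 0.343) = 0.544.
- Difference: 5.0 points.

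| True median (weeks) | f = 10% | f = 20% | f = 30% |
|---|---|---|---|
| 16 | 0.351 → 0.375 (2.5) | 0.348 → 0.399 (5.1) | 0.345 → 0.425 (8.0) |
| 24 | 0.497 → 0.521 (2.4) | 0.494 → 0.544 (5.0) | 0.492 → 0.568 (7.7) |
| 32 | 0.592 → 0.614 (2.2) | 0.590 → 0.634 (4.5) | 0.587 → 0.656 (6.9) |

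Differences in points are from unrounded values. If the end-of-treatment scan rule is ignored altogether, n = S(8) − f[S(8)−S(24)] and d = (1−f)[S(8)−S(24)], and the range becomes 3.0 to 11.1. A simulation of 40,000 responders per setting, with the same response and scan times, gave 2.5 to 9.2. I take roughly 2 to 9 points. The model leaves out the 4-week confirmation assessment, which lowers the differences a little.

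**3. How many patients?** Protocol 1.2.1.2.2 reports 3 partial responses in 114 evaluable patients; Amendment 3 gives 106 enrolled. Expected responders: 106 × 3/114 = 2.8. At assumed response rates of 5% and 10% they are 5.3 and 10.6. With 2.8 responders and f of 10 to 30%, 0.3 to 0.8 patients would be affected.

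Small numbers do not make one flag harmless. Take four invented responders who stop for progression at 2, 3, 4 and 6 months, those at 2 and 4 without a progression scan. With the PFS rule the curve steps through 0.75, 0.50, 0.25 and 0, and the median is 3 months. Censoring the two (at the stop date, for simplicity) gives 0.667 at 3 months and 0 at 6, and the median is 6 months.

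**The case against.** The protocol's calls for documented progression and prompt assessment mean that the mismatch mostly needs a missed scan or documentation by other means. SAP 4.3 is also the section that follows the protocol; 4.4 is the one that departs from it. DOR is a descriptive secondary endpoint, few responders are expected, and SAP 2.3 and 4.3 fall back to a listing when responses or events are few. All of this stands and limits the weight of the point. It does not remove the point, because these provisions make the case rarer without saying how to analyse it. A listing still needs an event/censor flag.

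It could also be said that documented progression already includes a stopping reason on the case report form. The wording of 4.4 tells against this: it adds the stopping reason to the same base event and confines the addition to PFS.

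Three stronger readings are tempting, and the documents do not support them.
- A reader might infer that the response table in SAP 4.2 has the same fault, showing patients as not evaluable who should be PD. But 4.2 says "Overall response is determined by investigator assessment for each tumor assessment in the study", and Appendix B assigns PD from lesions, so a stopping reason does not belong there. Table 7-1 note 3 requires a scan for patients who stop before the first scheduled one. SAP 4.4 also says "Patients who do not have any post baseline tumor assessment will be considered as censored at Day 1", so such a patient is not clearly a PFS event either.
- A reader might take the phase I gap between 132 treated and 114 evaluable (18/132, about 14%) as the share affected. But 132 − 111 = 21 of those treated had not discontinued, and the efficacy figures carry no cut-off date. Not evaluable does not mean early progression.
- A reader might expect the median DOR to jump by a full scan interval, from 24 to 40 weeks. This happens at a true median of 24 weeks only because the curve then sits almost exactly at one half at the week-24 scan. In the table, the 16-week and 32-week rows stay on the same side of one half with and without the rule.

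**Conclusion.** The point holds for DOR against PFS. As written, SAP 4.3 and 4.4 can classify the same responder differently, and the resulting censoring is informative and biases DOR upward. On an assumed 10 to 30% of progressions without an adequate scan, exponential DOR and the Table 7-1 scan times, the 26-week DOR rate is overstated by roughly 2 to 9 points. The documents do not give that share, so the size is conditional on it.

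In practice about 3 responders are expected at the phase I rate, and the likely visible effect is an event/censor flag in a listing. ORR and the primary Bayesian analysis of clinical benefit do not use DOR and do not change.

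**What to change.** - In SAP 4.3, add that progression given as the reason for stopping ribociclib also counts as a progression event for DOR.
- In both 4.3 and 4.4, state one event date for this case, for example the recorded date of discontinuation for progression. SAP 4.4 gives none at present, so a cross-reference from 4.3 would not be enough.
- In SAP 2.3, list this as an extension of the protocol's documented progression, for both PFS and DOR.

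The cost is a few sentences and reuse of the PFS derivation, with the date rule added. No new data are needed, and the response table in SAP 4.2 stays as it is.

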4.4 Progression Free Survival (PFS)

PFS is defined as the time from the date of first dose of ribociclib to the date of the first documented disease progression/relapse or death due to any cause within 30 days of the last study drug dose date, and is calculated as $PFS = (\text{date of progression/relapse or death} - \text{date of first study treatment} + 1)$. Disease progression noted as the reason for discontinuation of treatment will also be considered as a progression event for PFS analyses.

Patients who discontinue or complete study treatment without disease progression will be censored at last adequate tumor assessment on or before the discontinuation/completion of the study. For patients who are still on study treatment at the time of data cut-off date for the primary analyses, PFS will be censored at the last adequate tumor assessment before the data cut-off date for the analysis of PFS for the primary CSR. Patients who do not have any post baseline tumor assessment will be considered as censored at Day 1.

PFS will be summarized and graphed using the Kaplan-Meier product-limit method². The estimated median survival time, the corresponding 95% CIs³, and 25th and 75th percentiles will be provided. In addition, survival-rate estimates with 95% CIs will also be provided at time points, such as 1, 2, 3, 4, 5, 6, 9 and 12 months. Analyses will be based on all tumor types combined. For tumor types that have ten (10) or more patients, separate summaries will be performed by the tumor type.

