**Table 3-1      Objectives and related endpoints**

Objective	Endpoint	Analysis
Primary: To assess clinical benefit associated with ribociclib treatment based on local investigator assessment. For patients with solid tumors the assessment criteria will be RECIST 1.1 and will include responses of CR or PR or SD. For hematologic tumors other appropriate hematological response criteria will apply and are included in the appendices.	Clinical benefit rate (e.g. defined as CR or PR or SD $\geq$ 16 weeks for solid tumors)	Refer to Section 10.4
Key secondary: To assess Overall Response (OR) of Partial Response (PR) or greater based on local investigator assessment. For patients with solid tumors the assessment criteria will be RECIST 1.1 and will include responses of CR and/or PR. For hematologic tumors other appropriate hematological response criteria will apply and are included in the appendices.	Overall response rate (PR or greater)	Refer to Section 10.5.1
Other secondary: To assess Progression-Free Survival (PFS) based on local investigator assessment per RECIST 1.1 or other appropriate hematological response criteria To assess Overall Survival (OS) To assess Duration of Response (DOR) based on local investigator assessment per RECIST 1.1 or other appropriate hematological response criteria To assess safety and tolerability	Time from the date of first dose to the date of first documented disease progression or relapse or death due to any cause Time from the date of first dose to the date of death due to any cause Time from the first documented response to the date first documented disease progression or relapse or death due to any cause Incidence of adverse events (AEs), serious adverse events (SAEs), changes from baseline in vital signs, laboratory test results(hematology, biochemistry), ECG, and cardiac imaging will be assessed by the Common Terminology Criteria for Adverse Events (CTCAE), v4.03	Refer to Section 10.5.2 Refer to Section 10.5.2 Refer to Section 10.5.2 Refer to Section 10.5.3

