### 10.4.4 Handling of missing values/censoring/discontinuations

A patient who has not progressed or died at the date of the analysis cut-off would have his/her PFS and OS censored at the time of the last adequate assessment before the cut-off date. Any disease assessment indicating response status other than “unknown” or “not done” is considered an adequate response assessment.

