### 10.5.2 Other secondary efficacy objectives

The secondary objectives of the study:

- To assess progression free survival (PFS) based on local investigator assessment per RECIST 1.1 or other appropriate hematological response criteria
- To assess overall survival
- To assess duration of response (DOR) based on local investigator assessment per RECIST 1.1 or other appropriate hematological response criteria
- To assess safety and tolerability

The secondary efficacy variable progression free survival (PFS) is defined as the time from the date of first dose to the date of first documented disease progression or relapse or death due to any cause.

PFS will be summarized and graphed using the Kaplan-Meier product-limit method for each patient group. Patients who drop-out without progression will be censored at the time of last adequate assessment. The estimates of the 25th, median, 75th percentiles of the PFS and their 95% confidence intervals will be provided, if applicable.

Overall survival (OS) is defined as the time from the date of first dose to the date of death due to any cause. If a patient is not known to have died, survival time will be censored at the date of the last contact.

OS will be summarized and graphed using the product-limit method as above.

The duration of response applies only to patients whose best response was PR or CR. For patients with solid tumors the assessment criteria will be RECIST 1.1 and will include responses of CR and/or PR. For hematologic tumors other appropriate hematological response criteria will apply and are included in the appendices. The duration of response is defined as the time from the first documented response to the date first documented disease progression or relapse or death due to any cause. The duration of response will be summarized descriptively for each patient group.

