2.3 Change in planned analyses from the protocol

Cardiac imaging is only collected post baseline where clinically indicated and the value and potential abnormality will only be listed, and not summarized.

Summaries will be conducted for all patients combined with the following exceptions –

- Primary efficacy analysis on the clinical benefit via Bayesian hierarchical model
- Other clinical benefit and tumor response summaries for tumor types that have 10 or more patients enrolled.

In the event of a low response rate, DOR will be listed only.

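### SAP 4.4 and 4.3 count a death in PFS and DOR only within 30 days of the last dose, an unlisted departure from the protocol's event definition; separately, protocol 7.1.2 contradicts the other scan-schedule passages

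*SAP*

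**What the plan says.** **Event definition.** In SAP 4.4 the PFS event is "disease progression/relapse or death due to any cause within 30 days of the last study drug dose date". In SAP 4.3 the DOR event is "first documented progression/relapse or death due to any cause within 30 days of the last study drug dose date". The wording leaves open whether the window also governs progression, but on either reading it limits deaths. SAP 4.4 adds: "Patients who do not have any post baseline tumor assessment will be considered as censored at Day 1".

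Protocol Table 3-1 gives PFS as "Time from the date of first dose to the date of first documented disease progression or relapse or death due to any cause". Protocol 10.5.2 repeats "first documented disease progression or relapse or death due to any cause" for PFS and uses an equivalent event for DOR; 7.2.1 agrees. None sets a window.

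**Censoring.** Protocol 10.4.4 says "A patient who has not progressed or died at the date of the analysis cut-off would have his/her PFS and OS censored" at the last adequate assessment. Protocol 10.5.2 says "Patients who drop-out without progression will be censored at the time of last adequate assessment".

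**Declared changes.** SAP 2.3 covers cardiac imaging, pooling of summaries, and DOR ("In the event of a low response rate, DOR will be listed only"). It does not mention the death window.

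**Scan schedule.** The protocol summary, 4.1.1, Table 7-1 and 7.2.1.1.4 require scans every 8 weeks to week 16 and every 16 weeks after that. Table 7-1 applies this to the myeloma tests too. Section 7.2.1.2.3 (lymphoma) makes the reduction optional. Section 7.1.2 requires scans every 8 weeks and permits 12-weekly scans only after at least 4 post-baseline assessments in clinically stable patients, with myeloma exempt.

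**The concern.** A patient who stops without documented progression and dies more than 30 days after the last dose is a PFS event under the protocol's definition and a censored observation under the SAP. The two documents can therefore give different event counts from the same data. SAP 2.3 is where a reader would look for such a change, and it is not there.

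The protocol does not settle these patients either. Its event definition counts the death, its drop-out sentence censors the patient, and nothing says which prevails.

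The scan schedule is a separate conflict within the current protocol text. Progression is mostly dated by scans, and SAP 4.4 gives 6-month PFS as one of its time points.

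**Working it through.** The plan gives no figure to reproduce here: PFS and DOR are descriptive (SAP 2.2) and unpowered (SAP 7). The size was therefore found by simulation under stated assumptions.

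**1. Who changes status.** Only a patient who (a) stops without documented progression, (b) dies more than 30 days after the last dose, and (c) is still in survival follow-up. Protocol 4.1.2 exempts patients who withdraw consent or are lost, and 7.1.4.3 allows survival follow-up to end if the primary endpoint is not met.

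**2. Rate of such stops.** The documents give none for this trial. First-in-human study (protocol 1.2.1.2.1): 132 treated, 111 stopped, 96 for progression, so 111 - 96 = 15 for other reasons (8 adverse event, 3 consent, 1 lost, 3 not listed). Leaving out consent withdrawal and loss, which fail condition (c): 15 - 3 - 1 = 11, and 11/132 = 8.3%.

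**3. Death-rule simulation** (400,000 patients per setting, results scaled to the 106 enrolled). Assumptions:
- exponential progression with 16-week PFS of 0.25, 0.35 or 0.50;
- 8.3% assigned a non-progression stop, uniform over weeks 1 to 16 (about 4 to 6% actually stop that way, because progression comes first in the rest);
- exponential death after stopping, median 12, 24 or 36 weeks;
- scans at weeks 8, 16, 32 and 48, plus the end-of-treatment scan that Table 7-1 footnote 3 requires;
- 0, half or all of progression found off schedule;
- follow-up of 16 to 56 weeks at the CSR cut-off.

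Six months by SAP 2.5.8 is 6 x 30.3475 / 7 = 26.0 weeks.

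| Progression found off schedule | SAP minus protocol, 6-month PFS (points) |
|---|---|
| none | about +0.3 to +1.9 |
| half | about -0.2 to +1.1 |
| all | about -0.5 to +0.5 |

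Between 1.5 and 3.5 of 106 patients change from event to censored, out of roughly 70 to 98 events under the protocol definition. Standard error: sqrt(p(1-p)/106) = 4.2 points at p = 0.25 and 4.9 at p = 0.50.

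The sign varies because the protocol rule keeps these patients event-free until death and then counts them, whereas the SAP rule removes them at the last scan and treats them like those still at risk.

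**4. DOR.** At the first-in-human response rate (3 of 114, protocol 1.2.1.2.2), 106 x 3/114 = 2.8 responders; 2.8 x 8.3% = 0.23 stopping without progression. The effect is near zero.

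**5. Scan calendars.** 16-week passages: weeks 8, 16, 32, 48. Section 7.1.2 with the earliest permitted reduction: weeks 8, 16, 24, 32, 44. They agree to week 16, so CBR is unaffected. They part at week 24, just before week 26.0.

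**6. Schedule simulation.** Same set-up, every patient on one schedule. Each cell is 6-month PFS under 16-weekly scans minus that under 7.1.2, in points:

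| 16-week PFS | none off schedule | half | three quarters | all |
|---|---|---|---|---|
| 0.25 | +12.3 | +4.7 | +1.7 | -1.0 |
| 0.35 | +14.2 | +5.1 | +1.6 | -1.6 |
| 0.50 | +14.5 | +5.3 | +1.2 | -2.4 |

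**The case against.** **The SAP may only be clarifying.** The patients at issue are drop-outs without progression, and read literally protocol 10.5.2 already censors them; 10.4.4 does not say that nobody else is censored. This stands in part. A reader might infer that the protocol plainly counts these deaths and that the SAP breaks it, but the text does not go that far. Even so, the 30-day limit appears nowhere in the protocol's event definitions, and a reader of SAP 2.3 is not told of it.

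**The window has a rationale.** There is no efficacy follow-up after treatment (protocol 7.1.4.2), so counting every death adds some that occur long after the last scan. This stands, and it is why neither version should simply replace the other.

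**A reader might infer a material bias in PFS.** Larger gaps, up to about 10 points at 6 months, appear if 10 to 30% of patients stop without progression, no scan is done at stopping and follow-up runs to 104 weeks. Footnote 3 of Table 7-1 requires an end-of-treatment scan for those who stop before the first scheduled one, which should also make Day 1 censoring uncommon. Using 15/132 instead of 11/132 would bring in patients who are exempt from survival follow-up.

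**A reader might take +12 to +15 points as the schedule effect.** That needs no progression to be found off schedule. Protocol 7.2.1 requires prompt assessment on suspicion, footnote 3 requires end-of-treatment scans, and SAP 4.4 counts progression given as the reason for stopping.

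**Section 7.1.2 refers to Table 7-1 for details.** It does, but it still states its own mandatory 8-weekly interval, so the pointer does not remove the conflict.

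**Conclusion.** Both points hold, with limited consequences. The SAP narrows the PFS and DOR event without saying so in SAP 2.3, and the protocol leaves late deaths among drop-outs unresolved.

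On the assumptions above, about 1.5 to 3.5 of 106 patients change status and 6-month PFS shifts by about -0.5 to +1.9 points, below the standard error and with no fixed direction. DOR is practically unaffected. OS does not use the window, and the CBR decision does not depend on it.

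The scan-schedule conflict could matter more for 6-month PFS: about +5 points if half of progression is found off schedule, and +2 to -2 if three quarters or more is. The figure of +12 to +15 is only an upper bound. The documents do not give the off-schedule share, so no single value can be stated.

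**What to change.** **Late deaths.** State in protocol 10.5.2 and SAP 4.3 and 4.4 one rule for a patient who stops without progression and dies later, including one with no post-baseline scan.

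**Reporting.** Give PFS twice, each version labelled: with all deaths counted, as in the protocol's event definition, and with the 30-day window. List and justify the window in SAP 2.3.

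**Scan schedule.** Reconcile protocol 7.1.2 and 7.2.1.2.3 with the summary, 4.1.1, Table 7-1 and 7.2.1.1.4, including the treatment of myeloma. This review takes no position on which interval is right.

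**Cost.** Wording in a few sections and one re-run on data already collected; SAP 5.2 already lists all deaths and notes those within 30 days of the last dose. The downside is that all-death PFS includes some deaths long after the last scan and depends on how long survival is followed. Reporting both versions makes that visible.

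### SAP 4.4 censors patients without a post-baseline tumor assessment at Day 1 and does not exempt those who already have a PFS event

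*SAP*

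**What the plan says.** SAP 4.4 first defines the PFS events. Besides documented progression or relapse, it counts "death due to any cause within 30 days of the last study drug dose date", and it adds: "Disease progression noted as the reason for discontinuation of treatment will also be considered as a progression event for PFS analyses". Neither of these two needs a scan.

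The next paragraph gives the censoring rules. The first is conditional: "Patients who discontinue or complete study treatment without disease progression will be censored at last adequate tumor assessment on or before" the end of the study. The second covers patients still on treatment at the cut-off. The last carries no condition on event status: "Patients who do not have any post baseline tumor assessment will be considered as censored at Day 1".

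The other censoring rules in the documents are conditional on having no event:

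- Protocol 10.4.4: "A patient who has not progressed or died at the date of the analysis cut-off would have his/her PFS and OS censored" at the last adequate assessment.
- Protocol 10.5.2 counts progression, relapse or any death as an event, and censors patients who drop out without progression.
- SAP 4.3, for duration of response: "If a patient has not had an event, duration is censored at the date of last adequate tumor assessment".

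SAP 2.3, which lists changes from the protocol's planned analyses, mentions no change to PFS censoring.

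**The concern.** Outside leukemia, the first scheduled on-treatment disease assessment is at week 8. Take a patient who dies on treatment in week 5, or who is stopped for clinical progression in week 6 and is never scanned. The event paragraph makes this patient a PFS event. The last censoring sentence makes the same patient censored at Day 1. The SAP does not say which rule wins, so the programmer has to choose.

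If the censoring sentence wins, known early failures leave the Kaplan-Meier risk set before they can count, and the later curve is too high. SAP 4.4 reports PFS rates from month 1 onward, and separately for tumor types with ten or more patients. The early rates and the small cohorts are where a few such patients matter most.

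**Working it through.** **1. The rules side by side**, for a patient with no post-baseline tumor assessment:

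| Situation | SAP 4.4 event paragraph | SAP 4.4 last censoring sentence | Protocol 10.4.4 / 10.5.2 |
|---|---|---|---|
| Death within 30 days of last dose | Event | Censored at Day 1 | Event |
| Stopped, progression given as reason | Event | Censored at Day 1 | Not among those censored, if this counts as progression |
| No event | Not an event | Censored at Day 1 | Censored |

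The first two rows conflict inside SAP 4.4. Only the third row is consistent.

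**2. Size under the literal reading.** The plan states no PFS rate, median or event count, so there is no figure to reproduce. Let n patients include k early failures without a scan, with p = k/n, and assume no other censoring before the last of them. If m patients are still event-free at a later time t:

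- early failures counted as events: S(t) = m/n
- early failures censored at Day 1: S(t) = m/(n − k)
- ratio = n/(n − k) = 1/(1 − p)

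The documents do not give p. For an assumed range, and a true rate of 50%:

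| p (assumed) | 1/(1 − p) | True 50% is reported as |
|---|---|---|
| 5% | 1.05 | 0.50/0.95 = 52.6% |
| 10% | 1.11 | 0.50/0.90 = 55.6% |
| 15% | 1.18 | 0.50/0.85 = 58.8% |

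On the 106 patients enrolled (protocol, Amendment 3; the size of the full analysis set is not given), 5% to 15% is about 5 to 16 patients. In a tumor type with ten patients, one such patient gives 10/9 = 1.11 and two give 10/8 = 1.25.

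**3. Illustration with 8-weekly scans.** Assumptions: n = 106; early failures spread over days 8 to 52; 45% of the remaining patients progress at day 57; 40% of those left progress at day 113.

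| k (share) | 1 month: event vs Day 1 | 2 months | 4 months | Median (day) |
|---|---|---|---|---|
| 5 (4.7%) | 97.2% vs 100% | 52.8% vs 55.4% | 32.1% vs 33.7% | 113 vs 113 |
| 11 (10.4%) | 94.3% vs 100% | 49.1% vs 54.7% | 29.2% vs 32.6% | 57 vs 113 |
| 14 (13.2%) | 93.4% vs 100% | 48.1% vs 55.4% | 29.2% vs 33.7% | 57 vs 113 |

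For k = 11, 95 patients remain and 43 progress at day 57, leaving 52: 52/106 = 49.1% against 52/95 = 54.7%. The 2- and 4-month rates rise by exactly 1/(1 − p). The median either stays put or jumps a whole scan interval, depending on the assumed scan results.

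**4. If events take precedence**, the last sentence reaches only the third row of the first table, and the factor is 1.

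**The case against.** The strongest reply is that the sentence was meant only for event-free patients. The two sentences before it concern patients who stop without progression or are still on treatment, and censor them at the last adequate assessment. The Day-1 sentence then supplies a date where no such assessment exists. That is a natural reading and it produces no bias. It stands as a possible intent, but the condition that would secure it appears in the first sentence of the paragraph and not in the last.

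The group is also limited. A footnote to protocol Table 7-1 requires a tumor assessment at end of treatment for patients who stop before the first scheduled one. Section 7.2.1 requires prompt assessment when progression is suspected. Section 5.2 requires a life expectancy of at least 16 weeks. These rules shrink the group but cannot capture an early death or a patient who is never scanned.

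A reader might infer more than the documents support:

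- *That the plan certainly discards early failures.* It does so only if the last sentence is applied over the event definition.
- *That the two rules collide on every patient stopped for progression.* A patient with a non-progression scan at week 8 who later stops for clinical progression has a post-baseline assessment and is untouched.
- *That all these patients are failures in the primary endpoint.* Without a scan, SAP 4.1 recognizes progression in two cases only: when it is the recorded reason for stopping, and when it caused a death on treatment. It does not cover an early death from another cause.
- *That PFS is inflated against a historical benchmark.* Historical rates are specified only for clinical benefit.
- *That the median is overstated by a predictable percentage.* That needs a smooth survival curve, which 8-weekly scans do not give.

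**Conclusion.** The sentence is wrong as written. It contradicts two event rules in its own section and the protocol's censoring rules, and the SAP declares no departure from the protocol. Applied literally, it raises every PFS rate after the last early failure by 1/(1 − p), which is 1.05 to 1.18 for p of 5% to 15%. That range is an assumption, and the exact factor assumes no other early censoring. Under the event-first reading the effect is nil.

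The consequence is contained. SAP 2.2 makes all analyses other than the primary one descriptive, and no success or futility decision uses PFS. The primary Bayesian analysis of clinical benefit is unaffected. Still, a reported secondary endpoint should not rest on an unrecorded programming choice.

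**What to change.** Replace the last censoring sentence of SAP 4.4 with: *Patients with no PFS event and no post-baseline tumor assessment will be censored at Day 1.* Add that PFS events take precedence over this rule, and that progression recorded only as the reason for stopping is dated at the discontinuation date. Deaths need no new rule, since the SAP 4.4 formula already uses the date of death.

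The cost is a short text edit and a check of the PFS program. No new data are needed. If events were always meant to take precedence, no result changes; otherwise PFS estimates become somewhat less favorable.

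SAP 4.3 does not carry over the rule that counts progression as the reason for stopping. That is a separate consistency point for duration of response. Responders necessarily have a post-baseline assessment, so the Day-1 rule does not reach them.
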